8.2 SETTING

The surveys will be conducted in 5 countries (France, UK, Italy, Finland and Norway). [Table 1](#) below shows the home infusion patient and prescriber numbers for the 10 markets in which Fabrazyme home infusion is most prevalent as provided by MAH.

Table 1 - Approximate number of patients and prescribers for top 10 countries based on data provided by the MAH, as of February 2017

Country	Potential home infusion prescribers	Fabrazyme home infusion patients
France	30	140
UK	20	190
Italy	10	65
Finland	15	27
Norway	8	34
Germany	5	7
Spain	1	1
Netherlands	1	35
Sweden	3	10

Country	Potential home infusion prescribers	Fabrazyme home infusion patients
Belgium	5	10
TOTAL	98	519

The countries selected for this study had the highest number of prescribers of Fabrazyme home infusion or patients receiving Fabrazyme in the home setting based on the data in table 1. There are:

- 98 prescribers of Fabrazyme home infusion and 83 of these (85%) were based in France, UK, Italy, Finland and Norway.
- 519 Fabrazyme home infusion patients and 456 of these (88%) were based in France, UK, Italy, Finland and Norway.

Other markets (Germany, Spain, Netherlands, Sweden and Belgium) only had a maximum of 5 prescribers of Fabrazyme home infusion.

8.3 VARIABLES

The HCP and patient surveys will be comprised of

- A) Screening section for eligibility and demographics
- B) Main questionnaire for eligible subjects.

These items and the variables collected are described in detail in sections 8.3.1 to 8.3.4.

8.3.1 HCP screener

Screener data will be entered into the online survey link either by a member of the local fieldwork agency, asking the HCP screening questions over the phone, or independently by the HCP via the online link. All data entered will be captured on the online server to be downloaded at the end of fieldwork.

Table 2 - Overview of HCP screening questions*

Section	Content
Section 1	Survey introduction

Section	Content
Section 2	Demographics and screening questions 
 • Specialty • Years of experience treating Fabry disease • Years of experience prescribing Fabrazyme home infusion • Practice setting • Hospital type • Fabry disease patient workload (# patients seen in last 1 year) • Personal responsibility to prescribe Fabrazyme

*Content included, but not limited to the items included in the table

8.3.2 HCP Survey Questionnaire

Upon informed consent from the HCP, eligible HCPs will be provided a link to access and complete the main survey. Data will be entered online independently by the HCP. All data entered will be captured on the online server to be downloaded at the end of fieldwork.

Table 3 - Overview of HCP main survey questions*

Section	Content
Section 1	Key performance indicators 
 • Awareness of materials • Which materials have been received • Have materials been read • Overall usefulness rating of materials • Comprehensiveness of the key sections in education materials • Sources of information for home infusion
Section 2	Evaluation for home infusion and training 
 • Use of materials to evaluate and select patients for home infusion • Criteria required for a patient to be deemed eligible (knowledge assessment) • Are patients trained on home infusion process • Use of materials for training on home infusion process • Frequency key areas are covered in training • Steps taken in case of IAR (knowledge assessment) • Frequency of reviewing patients home infusion administration • Helpfulness of materials when reviewing home infusion administration

Section	Content
Section 3	Implementation of the logbook 
 • Frequency of completing administration details in logbook • Frequency of reviewing patients logbook • Was patient trained on logbook • Frequency of documenting changes, checking infusion rate and dose administered in logbook • Frequency logbook is discussed with patient/caregiver • Action taken if IARs recorded in Logbook • Key responsibilities of physician

*content included, but not limited to items in table

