8.3.4 Patient Survey Questionnaire

Upon informed consent from the patient, eligible patients will be passed a link to access and complete the main survey. Data will be entered online independently by the patient. All data entered will be captured on the online server to be downloaded at the end of fieldwork.

Table 5 - Overview of patient main survey questions*

Section	Content
Section 1	Key performance indicators 
 • Materials provided by physician • Which materials were received • Have materials been read • Involvement of infusion nurse or other medical trained professional • Frequency in which materials are referenced
Section 2	Understanding and knowledge of educational materials 
 • Overall usefulness rating of materials • Ease of understanding of the key sections in education materials • Knowledge assessment of preparation, administration and storage of Fabrazyme • Frequency key preparation and administration steps conducted
Section 3	Implementation of the logbook and handling AR 
 • Frequency in which logbook is completed and taken to appointments • Frequency Infusion changes reported in logbook • Familiarity with side effects/risks associated with home infusion • Sources of information for learning about side effects/risks • Action taken in case of AR (knowledge assessment) • Reporting side effects in logbook • Frequency logbook discussed with physician • Usefulness of logbook • Sources of information for home infusion

*content included, but not limited to items in table

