8.7 DATA ANALYSIS

The analysis will be cross-sectional and descriptive. Categorical data will be summarized by counts and percentages. Continuous data will be summarized using number, median, minimum and maximum values. Missing data will be noted for each variable.

A **positive outcome** reported across key pre-defined questions for each of these objectives would support the effectiveness of the educational material. For this assessment, a positive outcome is defined as at >70% of the survey participants providing a ‘correct’ response (specific questions and responses are outlined in Tables [Table 8](#) and [Table 9](#)). The 70% cut point is based on previous experience from other surveys evaluating the effectiveness of educational materials.

Table 8 - Questions to assess effectiveness in HCP survey

Category of assessment	Question text [Answer options]	Criteria for 'effective assessment'
To assess if materials are being received and read	A2. Which of the following material have you received or had access to? Select all that apply 1. Summary of Product Characteristics (SMPC) 2. Fabrazyme Home Infusion Therapy: A guide for Healthcare professionals treating patients with Fabry disease 3. Fabrazyme Home Infusion Therapy: Manual for Patients with Fabry disease who receive home infusion of Fabrazyme 4. None of the above	Majority of HCPs selecting Code 2
	A3. Have you read the Fabrazyme (agalsidase beta) home infusion educational materials? 1. Yes 2. No	Majority of HCPs selecting Code 1
To assess evaluation of home infusion	B1. Do you use the educational materials to evaluate and select patients for home infusions? 1. Yes 2. No	Majority of HCPs selecting Code 1
	B2. Which of the following criteria must be fulfilled before a patient is deemed eligible for Fabrazyme (agalsidase beta) home infusion? Select all that apply 1. Patient must be medically stable 2. A comprehensive evaluation must be completed before deciding on transfer of therapy to home infusion 3. Patient must have received Fabrazyme infusions for several months in a controlled setting and previous infusions well tolerated 4. Don't know	Majority of HCPs selecting codes 1, 2 and 3
To assess level of training to patients/caregivers	B4. Do you use the Fabrazyme (agalsidase beta) home infusion educational materials when training the patient/caregiver on the home infusion process? 1. Yes 2. No	Majority of HCPs selecting Code 1

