8.9 LIMITATIONS OF THE RESEACH METHODS

The following section briefly describes potential limitations of the study and its design. These include:

- While best efforts will be made to recruit a relatively large proportion (~40%) of the eligible population of HCPs, it remains a small and finite population and we cannot be fully confident in representativeness.
- Patients/caregivers will be recruited via HCP referrals, there may be an element of HCP selection bias that takes place despite request for HCPs to refer all Fabrazyme home infusion patients making the population less generalizable. In addition, the types of patients who agree to participate may not be completely generalizable to the entire patient population.

To minimize the risk of bias from participating physicians the MAH will

- Contact all HCPs on the target list to recruit for patients (regardless of whether they take part themselves).
- Not ask that physicians have received the materials or that patients need to have received the materials upon recruitment
- Explain the purpose of the survey from a regulatory purpose in the invitation letter and not specifically mention it is to assess the education materials.

It is not possible to collect data on HCPs who decline participation, thus comparisons between participating with non-participating HCPs is not possible.

- The sample size is based on assumptions from previous experience with recruiting HCP and patients from similar surveys. However, despite best efforts for recruitment, the maximum sample size may not be achievable given the limited universe of potentially eligible providers and patients due to the fact that Fabry disease is rare and the number of patients on home infusion is further limited.
- A full record of recruitment progress will be kept, including the number of respondents targeted, number of times contacted, reason for no participation, number of completes.

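### Knowledge items follow items that name the manual (and, for patient C5, logbook items) in unsupervised online surveys, so correct-answer rates may be overstated, and section 8.9 does not list this.

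*Protocol*

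**What the plan says.** Section 8.3.2 says of the HCP main survey that "Data will be entered online independently by the HCP"; section 8.3.4 says of the patient main survey that "Data will be entered online independently by the patient".

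Table 3 opens the HCP survey with items such as "Awareness of materials" and "Comprehensiveness of the key sections in education materials". The two knowledge assessments, on eligibility criteria and "Steps taken in case of IAR (knowledge assessment"), come in Section 2. Table 8 gives the wording: one A2 answer option is "Fabrazyme Home Infusion Therapy: A guide for Healthcare professionals treating patients with Fabry disease", A3 asks whether the materials have been read, and B1 asks whether they are used to select patients. B2 follows.

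Table 5 has the same structure for patients. Receipt, reading and frequency of reference come first, then usefulness and ease of understanding, then the preparation knowledge item (B3). "Action taken in case of AR (knowledge assessment"), which is C5, stands in Section 3 below the logbook-completion items.

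Section 8.7 counts an outcome as positive when more than 70% of participants answer correctly. Section 8.9 says that the invitation letter will "not specifically mention it is to assess the education materials". It does not mention cueing or look-up.

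**The concern.** The primary objective is the level of knowledge and understanding. The design is a single cross-sectional wave judged against a fixed cut point, with no pre-test or comparison group in which an order effect could cancel.

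A respondent who has just been shown the manual's title, and asked whether they have read and use it, has been pointed to the source before being tested on its content. Nobody supervises, so the manual can be opened. In patient C5, one keyed answer is to write the event up in the logbook, and C1 and C2 have just raised the logbook. Either route could lift the measured rate without any gain in knowledge. Order effects of this kind cannot be repaired after fieldwork.

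**Working it through.** **1. Order of the items (Tables 3, 5, 8 and 9)**

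- HCP B2 (eligibility): preceded by A2 and A3 (manual named; read) and B1 (used for selection). It comes before the training items B4 and B5 and before the logbook section.
- HCP B6 (steps in a reaction): preceded by the same items plus B4 and B5. B5c names reaction handling as a training topic but gives no steps. B5d mentions completing the logbook. The key is codes 1 and 3; the only option mentioning the logbook is code 2, which is not keyed.
- Patient B3 (preparation): preceded by A2, A3 and A5 and by the usefulness and ease-of-understanding items. It comes before the logbook section.
- Patient C5 (reaction): preceded by all of the above and by C1 and C2. The key is codes 2, 3 and 4; code 4 is the logbook option.

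All four items share exposure to the named manual. Only C5 has a keyed answer that an earlier item brings up. If the C5 key requires all three codes, a logbook cue can raise its rate only through respondents who would otherwise have chosen 2 and 3 and left out 4.

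**2. Check of the plan's own figures**

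The half-width is 1.96 × √(p(1−p)/n). At p = 0.70:
- n = 34: 1.96 × √(0.21/34) = 0.154, matching the 15.4% in Table 6.
- n = 18: 1.96 × √(0.21/18) = 0.212, matching the 21.2% in Table 7.

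The other rows of both tables also reproduce.

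**3. Smallest count that passes**

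- n = 34: 23/34 = 67.6% fails and 24/34 = 70.6% passes.
- n = 18: 12/18 = 66.7% fails and 13/18 = 72.2% passes.

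**4. Chance that one item passes**

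This is P(X ≥ 24) for n = 34 and P(X ≥ 13) for n = 18, with X binomial and p the measured correct rate:

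| p | n = 34 | n = 18 |
|---|---|---|
| 0.50 | 0.012 | 0.048 |
| 0.55 | 0.047 | 0.108 |
| 0.60 | 0.138 | 0.209 |
| 0.65 | 0.313 | 0.355 |
| 0.70 | 0.554 | 0.534 |
| 0.75 | 0.789 | 0.717 |
| 0.80 | 0.938 | 0.867 |
| 0.85 | 0.991 | 0.958 |

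**5. Effect of an assumed upward shift**

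- True 65%, shift of 5 to 10 points: 31% to 55-79% (n = 34); 35% to 53-72% (n = 18).
- True 60%, shift of 10 points: 14% to 55% (n = 34); 21% to 53% (n = 18).
- True 50%, shift of 5 points: 1% to 5% (n = 34); 5% to 11% (n = 18).
- True 80%, shift of 5 points: 94% to 99% (n = 34); 87% to 96% (n = 18).

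The pass rule is sensitive to a modest shift when true knowledge lies near 70% and much less so elsewhere.

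**The case against.** Four objections have force.

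- **Section 8.9 is not contradicted.** A reader might infer that the questionnaire undoes a concealment promised there. It does not. The measure concerns the invitation letter, is listed under bias from participating physicians, and has done its work before the questionnaire opens. Masking during completion is never promised.
- **The bias is not shown to run one way, or to touch every item alike.** A reader might infer that all knowledge items follow training and logbook content and are always pushed towards an effective result. B2 and B3 precede that content, and B6 precedes the logbook section. If the mention in B5d cues anything in B6, it points to an unkeyed option. Nothing listed before B2, B3 or B6 in Tables 8 and 9 gives away a keyed answer. Upward bias is plausible, through the pointer to the manual and the C5 cue, but it is not demonstrated.
- **Safeguards may exist elsewhere.** Tables 3 and 5 are declared to be overviews, the questionnaires are in appendices not available here, and section 8.8.1 promises clear instructions at each question. A screen lock or an instruction against look-up cannot be excluded. What can be said is that the protocol text states none; its fieldwork checks look for repeated patterns, straight-lining and overly fast completion, none of which detects look-up.
- **Re-ordering is not a complete cure.** The manual can be opened wherever an item sits. B6, C5 and C6 themselves mention the logbook, so asking C5 and C6 early may cue the self-reported logbook items, which also serve the primary objective.

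These points narrow the concern and belong in the fix. They leave standing the order itself, the C5 sequence and the silence of 8.9.

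**Conclusion.** The concern holds as a design weakness of moderate weight. Knowledge is measured after the source has been named, in an unsupervised setting, and for patient C5 after the logbook has been raised. Correct-answer rates may be overstated, and the limitations section does not say so.

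The size cannot be derived from the documents. The 5 to 10 point shift is an assumption, and a true rate of 65% was chosen because it lies just below the cut point, where the impact is large. The calculation also assumes independent answers, full samples of 34 and 18 for the item, and the same shift for the whole sample. It shows how sensitive the pass rule is; it does not estimate the bias.

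**What to change.** Before launch, in Tables 3 and 5 and in both questionnaires:

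1. Place HCP B2 and B6 and patient B3 directly after the screener, before any item that names the materials.
2. Place patient C5, then C6, before C1 and C2; most simply straight after B3, so that they also precede the items naming the manual. C5 goes first because the C6 stem mentions the logbook.
3. Block back-navigation past these items and add an instruction to answer from one's own knowledge. Leave wording and scoring unchanged.
4. List residual look-up in section 8.9 as a limitation.

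The cost is re-programming and renumbering, with no added length; the pilot and soft launch in section 8.8.1 can test the new order. Look-up is reduced but not excluded. Early C5 and C6 may cue the self-reported logbook items C1, C2 and C7. If that trade is unacceptable, move only B2, B6 and B3 and state the cueing of C5 and C6 as a limitation.

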8.3.3 Patient screener

Screener data will be entered into the online survey link either by a member of the local fieldwork agency, asking the patient screening questions over the phone, or independently by the patient via the online link. All data entered will be captured on the online server to be downloaded at the end of fieldwork.

Table 4 - Overview of patient screening questions*

Section	Content
Section 1	Survey introduction
Section 2	Demographics and screening questions 
 • Patient or caregiver completing survey • Age of patient • Setting in which Fabrazyme administered (home infusion vs hospital setting)

*Content included, but not limited to the items included in the table

8.3.4 Patient Survey Questionnaire

Upon informed consent from the patient, eligible patients will be passed a link to access and complete the main survey. Data will be entered online independently by the patient. All data entered will be captured on the online server to be downloaded at the end of fieldwork.

Table 5 - Overview of patient main survey questions*

Section	Content
Section 1	Key performance indicators 
 • Materials provided by physician • Which materials were received • Have materials been read • Involvement of infusion nurse or other medical trained professional • Frequency in which materials are referenced
Section 2	Understanding and knowledge of educational materials 
 • Overall usefulness rating of materials • Ease of understanding of the key sections in education materials • Knowledge assessment of preparation, administration and storage of Fabrazyme • Frequency key preparation and administration steps conducted
Section 3	Implementation of the logbook and handling AR 
 • Frequency in which logbook is completed and taken to appointments • Frequency Infusion changes reported in logbook • Familiarity with side effects/risks associated with home infusion • Sources of information for learning about side effects/risks • Action taken in case of AR (knowledge assessment) • Reporting side effects in logbook • Frequency logbook discussed with physician • Usefulness of logbook • Sources of information for home infusion

*content included, but not limited to items in table

8.4 DATA SOURCES

Data sources will include:

- HCP materials: Screener, Self administered online Survey questionnaire

Patient materials: Screener, Self administered online Survey questionnaire

The online interview is estimated to take approximately 10-15 minutes to complete. All data entered into the survey will be collected onto an online server.

8.5 STUDY SIZE

8.5.1 HCP sample size

Given the rarity of Fabry disease and the small prescriber and patient universe for Fabrazyme (agalsidase beta) home infusion as demonstrated in Table 1 in Section '8.2 Setting' we are limited in terms of sample sizes that we can feasibly achieve.

A total sample size of 34 HCPs (physicians and nurses) who prescribe, monitor, oversee the management, and/or provide in person medical supervision of patients on Fabrazyme home infusion will be recruited across key countries previously described in '8.2 Setting'. A minimum of 25 physicians will contribute to the overall HCP sample.

The sample size calculation is based on several factors/assumptions:

- Total number of eligible respondents (assumed to be n=83 based on Table 1)
- Assumption that the target list is high quality and contains up to date contact information and that all respondents have given consent to be contacted by a 3rd party (due to GDPR regulations coming in place in May 2018)
- Assumption of a response rate of 30-40% based on previous experience in recruiting via target list in similar therapy area
 - Example 1 – French study in Gaucher disease – 30-40 respondents were contacted to achieve 15 completes (38-50% response rate)
 - Example 2 – Italian study in Gaucher disease – 65 eligible respondents were contacted to achieve 13 completes (20% response rate)

Given ~83 prescribing physicians across the 5 markets for consideration and a response rate of 30-40%, the maximum physicians expected to take part is therefore 25-34. This sample size reflects ~40% of prescribers across the 5 markets where Fabrazyme (agalsidase beta) home infusion is most prevalent.

In addition to the physicians, the HCP survey will include nurses who are involved in providing in person medical supervision of patients on Fabrazyme home infusion. There are not robust estimates of the numbers of nurses available for recruitment in each country, but we anticipate being able to recruit nurses through the methods outlined in section 8.1.1 in the UK, Italy, France and Finland, based on country-based direction. All markets will be investigated and final inclusion will be confirmed once successful contacts and acceptance to participate has been achieved.

[Table 6](#) denotes the level of precision for a sample of 34 for a selection of response levels to a particular question

Table 6 - Precision estimates for the target HCP sample size (n=34) for 60, 70, and 80% correct response levels

Correct response percentage	Lower limit	Upper limit	Precision (+/-)
80%	66.6%	93.4%	13.4%
70%	54.6%	85.4%	15.4%
60%	43.5%	76.5%	16.5%

8.5.2 Patient sample size

A total sample size of 18 Patients and/or Caregivers will be recruited across key countries previously described in ‘8.2 setting’. Given the rarity of the patient universe we are targeting, the patient sample numbers included are driven primarily by feasibility.

Sample size feasibility the calculations were based on several factors/assumptions:

- Total number of eligible patients is assumed to be 456 based on France, UK, Italy, Finland and Norway data in Table 2
- The patient recruitment approach will be via HCP referrals
 - All HCPs contacted are asked to pass on details of the survey to eligible patients, however there is a higher likelihood that HCPs who participate will encourage their patients to also participate. Thus, most conservative patient reach estimate would be limited to the patients treated by these 34 HCPs (~40%) or 180 patients.
- Assumed that despite best efforts the patient response rate will be low based on:
 - Reliance on HCPs informing all Fabrazyme patients/caregivers of the study
 - Reliance of patients/caregivers in being proactive in responding to the invitation letters

Table 7 describes the level of precision for a sample of 34 for a selection of response levels to a particular question.

Table 7 - Precision estimates for the target patient/caregiver sample size (n=18) for 60, 70, 80% correct response levels

Correct response percentage	Lower limit	Upper limit	Precision (+/-)
80%	61.5%	98.5%	18.5%
75%	55.0%	95.0%	20.0%
70%	48.8%	91.2%	21.2%
60%	37.4%	82.6%	22.6%

